7.1.1 Primary Efficacy Endpoint

The primary efficacy endpoint is the proportion of patients alive and not requiring non-invasive or invasive ventilation (ie, not receiving high-flow nasal cannula, non-invasive positive pressure ventilation, invasive mechanical ventilation, or ECMO) at Day 28, with each dose (Phase 2) or the optimal dose (Phase 3) of FP-025 compared to placebo.

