3 STUDY DESCRIPTION

3.1 Summary of Study Design

This is a Phase 2/3, randomized, double-blind, placebo-controlled, multicenter study to evaluate the efficacy and safety of FP-025 in adult patients with severe to critical COVID-19 with associated ARDS. The patients in each phase (Phase 2 and Phase 3) will be analyzed separately.

Each phase will consist of a Screening Visit, Treatment Period, and Follow-Up Period for a total study duration of approximately 60 days.

3.1.1 Phase 2

After eligibility is confirmed, approximately 99 patients will be randomized in a 1:1:1 ratio to receive FP-025 100 mg BID, FP-025 300 mg BID, or placebo BID for 28 days. During Phase 2, randomized patients will be stratified by the use of invasive mechanical ventilation at the time of randomization (yes or no). At least one-third of patients should be on invasive mechanical ventilation to ensure that treatment benefits can be assessed for patients at different severity levels.

Patients with Grade 3 to Grade 4 heart failure, Stage 3 or greater COPD, persistent asthma, and mild liver disease (ie, Child-Pugh Class A) will not be excluded from the study. The independent Data Monitoring Committee (iDMC) will independently monitor safety of the entire population and in different subgroups and may make recommendations as it deems appropriate. During Phase 2, no limitation in enrollment of subgroups is expected, unless clear safety signals arise in those subgroups during iDMC reviews.

The reason for hospital admission, the standard of care followed for each patient and center, and whether any care decisions were based on resource limitations will be clearly documented for all patients beginning on Day 1 (Visit 2). All patients will be allowed to receive standard of care and/or emergency use authorization (EUA) medications and treatment for COVID-19; however, the study drug should be discontinued for other non-standard of care concomitant medications used with the intent of directly treating COVID-19 unless there is prior Medical Monitor or Sponsor approval for the patient to remain on the study drug. If the use of concomitant medications necessitates study drug discontinuation, the patient should be encouraged to remain in the study and to follow-up for key study visits (Day 28 and Day 60) but will not be required to attend every study visit. If the patient withdraws, he/she should complete the Early Termination Visit.

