4.2 Exclusion Criteria

Patients who meet any of the following criteria will be excluded from participation in the study:

1. Is not expected to survive more than 24 hours;
2. Is on extracorporeal membrane oxygenation (ECMO) at the Screening Visit;
3. Has an underlying clinical condition where, in the opinion of the Investigator, it would be extremely unlikely that the patient would come off ventilation (eg, motor neuron disease, Duchenne muscular dystrophy, or rapidly progressive pulmonary fibrosis);
4. Has a known history of idiopathic pulmonary fibrosis or interstitial lung disease as defined by the American Thoracic Society 2018 guidelines;²³
5. Has known active tuberculosis (TB), a history of incompletely treated TB, and/or suspected or known extrapulmonary TB;
6. Has Child-Pugh Class B or C active liver disease or an alanine aminotransferase or aspartate aminotransferase level $>4 \times$ the upper limit of normal at the Screening Visit;
7. Has moderate to severe renal insufficiency, defined as an estimated glomerular filtration rate (eGFR) ≤ 30 mL/min/1.73 m², at the Screening Visit or requires hemodialysis;
8. Has a malignant tumor (excluding a malignant tumor cured with no recurrence in the past 5 years, completely resected basal cell and squamous cell carcinoma of skin, and/or completely resected carcinoma in situ of any type);
9. Has an uncontrolled systemic or local autoimmune or inflammatory disease besides COVID-19;
10. Has evidence of an active concurrent non-COVID-19 pneumonia that requires additional antimicrobial treatment at the time of the Screening Visit and is caused by a known or suspected bacterial pathogen, respiratory syncytial virus (RSV), influenza virus, SARS-CoV-1, MERS-CoV, aspergillus, mucormycosis-causing fungi, or other pulmonary pathogen(s);
Note: If a viral respiratory panel has not been collected within the 24 hours prior to the Screening Visit, a viral respiratory panel will be administered at the Screening Visit to determine eligibility. At a minimum, the panel will evaluate for RSV, influenza A, and influenza B.
11. Has received any other investigational therapeutic products within 4 weeks or 5 half-lives, whichever is longer, prior to randomization;

12. Has a known history of HIV, hepatitis B, or hepatitis C infection;
13. Has a known serious allergic reaction or hypersensitivity to any components of FP-025;
14. Is pregnant or breastfeeding;
15. Has a history of drug or alcohol abuse within the past 2 years;

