9.2.1.1 Primary efficacy analysis

The primary efficacy endpoint is the proportion of patients alive and not requiring non-invasive or invasive ventilation (ie, not receiving high-flow nasal cannula, non-invasive positive pressure ventilation, invasive mechanical ventilation, or ECMO) at Day 28. The treatment group difference of the response proportions, along with the corresponding 95% confidence interval and p-value, will be provided using the logistic regression model by Guo et al. (2012)²⁴ and Ge et al. (2011),²⁵ adjusted for stratification factor (use of invasive mechanical ventilation at the time of randomization [yes or no]). Additional prognostic baseline covariates (eg, age, region, body mass index) may be added as covariates/factors into the model to increase precision in the estimation of difference in proportions. Details will be provided in the SAP.

The primary analysis will be repeated on the PP Population.

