9.2.5 Sample Size Determination

For the Phase 2 study, approximately 99 patients will be randomized in a 1:1:1 ratio to 1 of 3 treatment groups: FP-025 100 mg BID, FP-025 300 mg BID, or placebo BID. No formal statistical assessment for sample size determination has been performed. The sample size is considered adequate to provide the necessary data to evaluate the objectives of the study.

For Phase 3, a total of 304 patients (152 patients per treatment group) will provide approximately 80% power to detect a 15% improvement in response rate, based on a control response rate of 60% and assuming a response rate of 75% with the study drug treatment group, using a 1-sided 0.025 level test. The sample size estimate assumes that an interim analysis will be conducted after approximately 70% of patients (approximately 213 patients) have completed the EOT Visit on Day 28 or have discontinued early, but would have reached Day 28 had they remained in the study, to assess early futility and potential sample size recalculation. The sample size was calculated using EAST 6.4. The Phase 3 sample size will be formally recalculated based on results from the Phase 2 part of the study. A maximum of 608 patients may be included. If the iDMC, in consultation with the Sponsor determines that a sample size of more than 608 patients is needed, a protocol amendment will be required.

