C4M = neo-epitope of MMP-2, 9, and 12-mediated degradation of type IV collagen; C6M = neo-epitope of MMP-2-mediated degradation of type VI collagen; CRPM = neo-epitope of MMP-1 and 8-mediated degradation of C-reactive protein; IL = interleukin; MMP = matrix metalloproteinase; PRO-C3 = released N-terminal pro-peptide of type III collagen; PRO-C4 = internal epitope in the 7S domain of type IV collagen; PRO-C6 = C-terminal of released C5 domain of type VI collagen α3 chain (endotrophin); reC1M = neo-epitope of MMP-2, 9, and 13-mediated degradation of type I collagen; X-FIB (D-dimer) = neo-epitope of plasmin-mediated degradation of cross-linked fibrin.

APPENDIX C: NATIONAL INSTITUTE OF ALLERGY AND INFECTIOUS DISEASES 8-POINT ORDINAL SCALE FOR COVID-19 AND HOSPITALIZATION OUTCOMES

Table 4. NIAID 8-Point Ordinal Scale for COVID-19 and Hospitalization Outcomes

Numerical Score	Definition
1	Death
2	Hospitalized, on invasive mechanical ventilation or extracorporeal membrane oxygenation
3	Hospitalized, on non-invasive ventilation or high-flow oxygen devices
4	Hospitalized, requiring supplemental oxygen
5	Hospitalized, not requiring supplemental oxygen – requiring ongoing medical care (COVID-19-related or otherwise)
6	Hospitalized, not requiring supplemental oxygen – no longer requires ongoing medical care
7	Not hospitalized, limitation on activities and/or requiring home oxygen
8	Not hospitalized, no limitation on activities

COVID-19 = coronavirus disease 2019; NIAID = National Institute of Allergy and Infectious Diseases.
Source: Adaptive COVID-19 treatment trial (ACTT). NIH clinicaltrials.gov website.
<https://clinicaltrials.gov/ct2/show/NCT04280705>. Accessed 09 November 2020

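### The primary endpoint makes no exception for CPAP or bilevel support used before COVID-19, so a recovered home user can be scored a failure

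*Combined protocol and SAP*

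**What the plan says.** Section 7.1.1 sets the primary endpoint as the "proportion of patients alive and not requiring non-invasive or invasive ventilation (ie, not receiving high-flow nasal cannula" and continues with the other devices on the list. The lead word is 'requiring', but the clause in brackets turns it into 'receiving': "not receiving high-flow nasal cannula, non-invasive positive pressure ventilation, invasive mechanical ventilation, or ECMO) at Day 28". The Synopsis and section 9.2.1.1 repeat the definition. Section 7.1.2 applies it at Day 60, where it is step 3 of the testing hierarchy in section 9.2.1.3. None of these places mentions support used before the illness.

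On who may enrol, section 3.1.1 states that "Patients with Grade 3 to Grade 4 heart failure, Stage 3 or greater COPD, persistent asthma, and mild liver disease" are not grounds for exclusion. No criterion names home CPAP or bilevel support. The nearest is exclusion 3 in section 4.2, which applies when, in the Investigator's opinion, "it would be extremely unlikely that the patient would come off ventilation (eg, motor neuron disease, Duchenne muscular dystrophy" and rapidly progressive pulmonary fibrosis being the examples. Exclusion 18 is a general discretion.

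The ordinal scale in Appendix C, Table 4 treats the same support differently. Score 3 is "Hospitalized, on non-invasive ventilation or high-flow oxygen devices", so non-invasive ventilation counts only in hospital. A discharged patient scores 7 or 8, and 8 is "Not hospitalized, no limitation on activities".

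**The concern.** The endpoint is meant to capture recovery from COVID-19 respiratory failure. Consider a patient who used positive pressure support at home before admission, was intubated, recovered, went home and resumed the usual nightly support. Under the bracketed clause this patient has the same primary result as one still intubated at Day 28.

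Other measures in the plan record the patient as recovered: NIAID 7 or 8, alive and not hospitalized, and days free of invasive ventilation (section 7.1.3). In Table 3 the status score scheduled for discharged patients is the NIAID scale, which cannot show home positive pressure. A site that works back from that score would record a responder. A site that works from the endpoint text would record a failure.

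At stake is some dilution of the treatment difference on the primary endpoint and on step 3 of the hierarchy, together with inconsistent scoring. Phase 2 is exposed too: with about 99/3 = 33 patients per arm, one patient scored the other way moves an arm's rate by 1/33 = 3.0 points, and those rates feed dose selection and the Phase 3 sample size.

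**Working it through.** **1. Does any other text supply the exception?** Section 9.2.1 leaves data handling and imputation to the SAP, and section 9.2.1.1 leaves the covariates to it. Neither defers the endpoint definition. The combined document includes no separate SAP text, so whether the SAP settles the point cannot be checked. Section 9.2.1 uses observed data whatever the intercurrent events. This patient's status is observed, so the imputation rules and the tipping-point analysis do not reach it.

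**2. Reproduce the stated sample size.** Section 9.2.5 gives 60% against 75%, 152 per arm, "using a 1-sided 0.025 level test", and about 80% power. With the pooled-variance test:

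power = Φ{ [ Δ√n − 1.96·√(2p̄(1−p̄)) ] / √(p₁(1−p₁) + p₂(1−p₂)) }

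with Δ = 0.15, n = 152 and p̄ = 0.675: (1.8493 − 1.2982)/0.6538 = 0.843, and Φ(0.843) = 80.0%. The same test needs 152 per arm, or 304.

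For Table 1, the unpooled drift is 0.15/√(0.4275/152) = 2.828. With futility at z ≤ 0.789 after 213/304 of the information and a final bound of 1.960, the futility probability is 0.785 under the null and 0.0572 under the alternative, and power is 80.2%. All of these agree with the plan. The sample size is sound on its own inputs.

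**3. Illustration of dilution.** Assumptions, none of them in the documents: 60% and 75% hold among patients without chronic support; a share f in each arm uses chronic support; they would otherwise respond at the same rates; and all are forced to failure. The rates become 0.60(1−f) and 0.75(1−f).

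| f | patients of 304 | rates | difference (points) | power, pooled | power with futility look | N for 80%, pooled |
|---|---|---|---|---|---|---|
| 0 | 0 | 60.0% / 75.0% | 15.0 | 80.0% | 80.2% | 304 |
| 1% | 3 | 59.4% / 74.25% | 14.85 | 78.8% | 79.0% | 314 |
| 2% | 6 | 58.8% / 73.5% | 14.7 | 77.6% | 77.7% | 324 |
| 5% | 15 | 57.0% / 71.25% | 14.25 | 73.8% | 73.9% | 354 |

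**4. The other reading of the planning rates.** If 60% and 75% are overall rates on the endpoint as written, any forced failures are already in them, and 304 patients give the stated 80%. The loss against the stated power is then zero.

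**The case against.** The strongest objection concerns power. A reader might infer from the table that the trial falls below its stated 80%. The documents do not support that. Section 9.2.5 gives 60% and 75% as response rates without saying that they leave out patients on chronic support, so step 4 is at least as natural a reading as step 3. The Phase 3 size is also to be recalculated from Phase 2 results on the same endpoint, and the interim analysis allows a promising-zone increase up to 608. Prevalence is not given anywhere, and the share may be very small. This objection stands in full.

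A reader might also infer that a home user can never be a responder. That is too strong. The lead word is 'requiring'. CPAP appears only in the weaning criteria of Appendix D, and no text says whether nightly home CPAP counts as non-invasive positive pressure ventilation. No hour window is set at Day 28, so night-only use might not be scored at a daytime visit. Exclusions 3 and 18 may remove some of these patients. This stands against 'never', but none of it supplies an exception. It shows that the scoring is unsettled, which is itself a reason to clarify.

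Two further points are fair. The NIAID scale is a separate measure and need not agree with a device-based endpoint for every patient, so the mismatch illustrates the gap and is not a contradiction. A strict device rule is also objective, whereas an exemption brings in some judgment.

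**Conclusion.** The gap in the definition is real. Taken literally, the rule scores a recovered patient on usual home support as a failure at Day 28 and Day 60, and the unsettled terms allow sites to differ. Randomization spreads such patients across the arms and nothing in the rule depends on treatment, so the consequence is non-differential misclassification that dilutes the difference. Bias between arms and Type I error inflation do not follow from the text.

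The size is unknown. On the assumptions of step 3, each 1% of patients affected costs about 1.2 to 1.3 points of power. On the reading in step 4 there is no loss against the stated figure. No shortfall from 80% is shown, and the point is best treated as a cheap improvement to the definition.

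**What to change.** Add one sentence to section 7.1.1, to the Day 60 key secondary endpoint and to the SAP: CPAP or non-invasive ventilation for a chronic condition documented before the COVID-19 illness, at no more than the pre-illness level, does not count as receiving non-invasive ventilation. State there also the period over which support is scored at Day 28 and Day 60.

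Add an item to the Screening medical history that records the type and level of any home support before the illness. It should be completed before randomization so that the exemption cannot depend on outcome. Score both time points against that record under the blind. The change should be in place before the Phase 2 primary analysis is unblinded.

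The cost is the sentence, one eCRF question, and the site's work in documenting earlier support. A small element of site judgment enters the comparison with the pre-illness level, and the response rate may rise slightly in both arms. The change concerns scoring only and does not touch patient care.

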7.1.2 Key Secondary Efficacy Endpoints

The key secondary efficacy endpoints include the following, with each dose (Phase 2) or the optimal dose (Phase 3) of FP-025 compared to placebo:

- Proportion of patients on invasive mechanical ventilation at Day 28;
- Proportion of patients alive at Day 28;
- Proportion of patients alive and not requiring non-invasive or invasive ventilation (ie, not receiving high-flow nasal cannula, non-invasive positive pressure ventilation, invasive mechanical ventilation, or ECMO) at Day 60;
- Proportion of patients on invasive mechanical ventilation at Day 60; and
- Proportion of patients alive at Day 60.

7.1.3 Other Secondary Efficacy Endpoints

The other secondary efficacy endpoints include the following, with each dose (Phase 2) or the optimal dose (Phase 3) of FP-025 compared to placebo:

- Quantitative assessment of lung fibrosis at Day 28 and at Day 60 using high-resolution, non-contrast CT scan;
- Proportion of patients who were randomized on invasive mechanical ventilation who are free of invasive mechanical ventilation at Day 28 and at Day 60;
- Number of ventilator-free days (ie, days free of invasive mechanical ventilation) at Day 28 and at Day 60;
- Number of ICU-free days at Day 28 and at Day 60;
- Number of days in the hospital at Day 28 and at Day 60;
- Change from baseline in peripheral capillary oxygen saturation (SpO₂) at Day 28 and at Day 60;
- Change from baseline in PaO₂/FiO₂ ratio at Day 28 and at Day 60 (patients on invasive or non-invasive ventilation only);
- Proportion of patients alive and not hospitalized at Day 28 and at Day 60;

- Proportion of patients with disease progression (defined as a ≥ 2 -point decrease in the NIAID 8-point ordinal scale score or death) at Day 28 and at Day 60;
- Proportion of patients who improve by ≥ 2 points on the NIAID 8-point ordinal scale scores at Day 28 and proportion of patients who improve by ≥ 2 points at Day 60;
- Pulmonary function at Day 28 (if possible based on the patient's clinical condition per the judgment of the Investigator) and at Day 60 (all patients) based on the following scores:
 - Forced vital capacity (FVC);
 - Forced expiratory volume in 1 second (FEV₁);
 - FEV₁/FVC ratios; and
 - Diffusing capacity of the lungs for carbon monoxide; and
- Change from baseline in eGFR, blood urea nitrogen, and serum creatinine at Day 28 and Day 60.

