According to the United States Centers for Disease Control (updated 30 June 2020), approximately 3% to 17% of COVID-19 patients develop ARDS. Among hospitalized patients, that number increases to 20% to 40%, and up to 67% to 85% for those admitted to the intensive care unit (ICU).⁷ ARDS is associated with mortality rates of approximately 40%;⁸ however, mortality from COVID-19-induced ARDS is even higher, with reported death rates of at least 50%.^{9,10} Computed tomography (CT) scanning of the lungs of ARDS survivors often demonstrates abnormalities similar to those seen in pulmonary fibrosis.¹¹ This is also consistent with findings from patients with previous SARS and MERS infections, many of whom exhibited post-viral pulmonary fibrosis.^{12,13} Although long-term lung fibrosis in recovered COVID-19 patients has not been studied in detail due to the recent emergence of the disease, it is reasonable to expect that pulmonary fibrosis will be a significant issue in patients recovering from COVID-19. In the literature, it was reported that histological features of lung fibrosis were found to relate to the duration of ARDS.¹⁴ Potential anti-inflammatory and anti-fibrotic treatments could probably benefit COVID-19 patients if given at early onset of ARDS.¹⁵

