9.2 Statistical Methods

9.2.1 Analysis of Efficacy

Patients who discontinue the study drug will remain in the study to have safety and efficacy assessments performed. Patients should be encouraged to follow-up for key study visits (Day 28 and Day 60) but will not be required to attend every study visit. The data observed on-study will be used for analysis regardless of any intercurrent events. Patients who die or discontinue treatment prior to the assessment time point (Day 28 or Day 60) because of lack of efficacy, and cannot have clinical status determined at the time point, will be considered treatment failures. Details regarding data handling and imputation method will be provided in the Statistical Analysis Plan (SAP).

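### Days in hospital has no rule for death, and under the plan's stated default an early in-hospital death would count as a short, favourable stay

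*Combined protocol and SAP*

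**What the plan says.** Section 7.1.3 (repeated in the synopsis) includes "Number of days in the hospital at Day 28 and at Day 60" among the other secondary efficacy endpoints, "with each dose (Phase 2) or the optimal dose (Phase 3) of FP-025 compared to placebo". It attaches no score, composite or competing-risk treatment for death.

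Two general rules in section 9.2.1 could apply:

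- "The data observed on-study will be used for analysis regardless of any intercurrent events".
- A treatment-failure rule for "Patients who die or discontinue treatment prior to the assessment time point (Day 28 or Day 60) because of lack of efficacy", limited to patients whose clinical status at the time point cannot be determined.

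Section 9.2.1 leaves data handling and imputation to the SAP, and section 9.2.1.2 does the same for the analysis of the other secondary endpoints. The supplied document contains no SAP text on hospital days.

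The same list has one hospital endpoint that does build in survival: "Proportion of patients alive and not hospitalized at Day 28 and at Day 60". It also has "Number of ICU-free days at Day 28 and at Day 60" and a ventilator-free-days endpoint. Neither states what happens to days after death.

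**The concern.** Fewer hospital days is naturally read as better. A patient who dies in hospital on Day 4 has about 4 observed days; a patient kept alive but still an inpatient on Day 28 has about 28. Neither general rule corrects this. Treatment failure is a category that suits a yes/no endpoint and assigns no value to a count. Nor is a dead patient's count missing: it is fully known, so an ordinary imputation rule would not reach it.

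Death will be common here. Section 1.1 says that "mortality from COVID-19-induced ARDS is even higher, with reported death rates of at least 50" per cent. At stake is whether a difference in hospital days can be read at all when mortality differs between the arms.

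**Working it through.** **The plan's own figure.** The documents give no figure for hospital days. The only sizing figure is for the primary endpoint, and it reproduces. With 60% against 75%, 1-sided 0.025, 80% power and pooled variance, n per group = [1.96·√(2·0.675·0.325) + 0.8416·√(0.60·0.40 + 0.75·0.25)]² / 0.15² = 151.9, so 152 per group and 304 in total. Nothing below changes it.

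**Inputs for hospital days.** All of these are assumptions, because the documents give no timings:

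- m: placebo mortality
- d: absolute mortality reduction on the drug, 0.10
- t: mean hospital days of patients who die, 8 or 12
- s: mean stay of patients who survive under either treatment
- L: mean stay of patients who survive only because of the drug, 20 days, or 28 (still in hospital at Day 28)

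All deaths are taken to occur in hospital, and the drug is taken not to change anyone else's stay.

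**Raw count.**

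- Placebo mean = m·t + (1 − m)·s
- Drug mean = (m − d)·t + (1 − m)·s + d·L
- Difference (drug minus placebo) = d·(L − t)

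Both m and s cancel. The size depends on the mortality difference and the two timings, not on the overall death rate.

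| t | L | Raw difference at Day 28 |
|---|---|---|
| 12 | 20 | 0.10 × 8 = +0.8 |
| 8 | 20 | 0.10 × 12 = +1.2 |
| 12 | 28 | 0.10 × 16 = +1.6 |
| 8 | 28 | 0.10 × 20 = +2.0 |

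A positive value means more days on the drug, so the drug looks worse. The sign is that of L − t: zero if L = t, and negative if deaths come later than the rescued patients' discharge.

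**Days alive and out of hospital to Day 28.** The difference is d·(28 − L): +0.8 for L = 20 and 0 for L = 28. A mortality benefit never pushes it the wrong way.

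**Second set of assumptions.** Mortality is 40% against 25%. These are the ceilings implied by the 60% and 75% response rates, since response requires being alive. Rescued patients have the same stay as other survivors.

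- Deaths at 8 days, survivors 18: placebo 0.40·8 + 0.60·18 = 14.0; drug 0.25·8 + 0.75·18 = 15.5; difference +1.5 against the drug. Days alive and out of hospital: 0.75·10 − 0.60·10 = +1.5 for the drug at Day 28, and 0.75·42 − 0.60·42 = +6.3 at Day 60.
- Deaths and survivors both 18: 0.15·(18 − 18) = 0.
- Deaths at 20, survivors 16: placebo 17.6, drug 17.0; difference −0.6, in favour of the drug. Days alive and out of hospital: 0.15·12 = +1.8, so the raw count still understates the benefit.

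**Simulation.** There were 4,000 trials of 152 per arm, with gamma-distributed stays, a Day 28 horizon and a 2-sided 0.05 t-test. With 40% against 25% mortality, deaths at 10 days and survivors 18, the raw count significantly favoured placebo in 22.7% of trials and the drug in 0.1%. Hospital-free days with death scored 0 favoured the drug in 44.8% and placebo in 0%. With deaths at 22 and survivors 14, the raw count favoured the drug in 11.5% and placebo in 0.3%. The percentages depend on the assumed distributions.

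**The case against.** The strongest reply is that the plan never commits to a raw count. Analysis of these endpoints is assigned to the SAP. The observed-data sentence follows text about patients who stop study drug, and the next sentence takes up deaths separately. That stands in part: the accurate statement is that no rule for death is given, not that a raw comparison is prescribed. But the variable is defined in section 7.1.3, the observed-data sentence is the only default that yields a number, and no supplied text replaces it.

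Several stronger readings are tempting and are not supported:

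- *A life-saving drug always looks worse.* The sign depends on assumed timings. A shorter stay in other survivors would also offset the shift: two days fewer gives −0.60 × 2 = −1.2 days at 40% placebo mortality or −0.50 × 2 = −1.0 at 50%, enough to cancel most or all of the +0.8 to +1.2 cases.
- *The high mortality in section 1.1 sets the size.* It cancels from the formula. The 60% planned control response also caps Day 28 placebo mortality at 40%, so a 50% scenario does not fit the sizing assumption.
- *A secondary objective rests on hospital days.* The mention of hospitalization outcomes in section 2.2 is part of the ordinal scale's name, as Appendix C shows, and that scale gives death the worst score.
- *An early death gets the best score in the trial.* It is among the best; a still earlier discharge scores lower.
- *The ventilator-free and ICU-free endpoints are already sound.* They have the same gap, because nothing stops days after death counting as free.

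It is also true that survival at Days 28 and 60 is tested in the Phase 3 hierarchy, and that the list already holds a survival-based hospital endpoint. Readers would therefore see mortality beside the day count.

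**Conclusion.** The point holds as a gap in the endpoint's definition. As written, the count has no rule for death, and the stated default treats an early in-hospital death as a short stay. With a 10-point mortality reduction, death at Day 8 to 12 and rescued stays of 20 to 28 days, the raw count moves against the drug by about 0.8 to 2.0 days at Day 28. With no mortality difference, there is no mortality-driven shift.

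A reader might infer that the trial's main conclusion is at risk. It is not: hospital days is outside the Phase 3 hierarchy, and the primary endpoint already requires survival. The harm is that a supportive endpoint cannot be interpreted when mortality differs. It should be corrected, but it does not affect the primary analysis.

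**What to change.** In section 7.1.3 and the synopsis:

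- Replace the endpoint with days alive and out of hospital through Day 28 and through Day 60, crediting 0 days after death and subtracting readmission days.
- Keep raw length of stay as a descriptive summary by vital status.
- State the same no-credit-after-death rule for ventilator-free and ICU-free days.

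Carry these definitions into the SAP before unblinding, so that the handling of deaths is not chosen after the results are seen.

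The cost is a wording change. The admission, discharge and death dates are already needed for the listed endpoints, and the sample size is unaffected. The downside is that length of stay as such becomes descriptive only. The new measure also has a limit: a survivor still in hospital throughout scores 0, the same as a patient who died in hospital, so it can be neutral to a survival benefit at Day 28.
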